11. DESCRIPTION OF GLOBAL AMENDMENT(S)

Number of global amendment	1	
Date of CTP revision	25 June 2018	
EudraCT number	2017-001107-71	
BI Trial number	1399-0002	
BI Investigational Product(s)	BI 1265162	
Title of protocol	Safety, tolerability and pharmacokinetics of multiple rising inhaled doses of BI 1265162 in healthy male subjects in a randomised, double blind, placebo-controlled trial	
To be implemented only after		
approval of the IRB / IEC /		
Competent Authorities		
To be implemented		
immediately in order to		
eliminate hazard –		
IRB / IEC / Competent		
Authority to be notified of		
change with request for		
approval		
Can be implemented without		
IRB / IEC / Competent		
Authority approval as changes		
involve logistical or		
administrative aspects only		
Section to be changed	Synopsis and 3.3.2 Inclusion Criteria No 2	
Description of change	Upper age was changed from 50 to 45 years	
Rationale for change	Request by CA	

c15848749-03 **Trial Protocol** Page 84 of 84

Proprietary confidential information © 2018 Boehringer Ingelheim International GmbH or one or more of its affiliated companies

Number of global amendment	2	
Date of CTP revision	04 July 2018	
EudraCT number	2017-001107-71	
BI Trial number	1399-0002	
BI Investigational Product(s)	BI 1265162	
Title of protocol	Safety, tolerability and pharmacokinetics of multiple rising inhaled doses of BI 1265162 in	
	healthy male subjects in a randomised, double	
	blind, placebo-controlled trial	
	omia, piaceoo-controlled trial	
To be implemented only often		
To be implemented only after		
approval of the IRB / IEC /		
Competent Authorities		
To be implemented		
immediately in order to		
eliminate hazard –		
IRB / IEC / Competent		
Authority to be notified of		
change with request for		
approval		
Can be implemented without		
IRB / IEC / Competent		
Authority approval as changes		
involve logistical or		
administrative aspects only		
and the second s		
Section to be changed	Flowchart	
Description of change	Planned time corrected on day 3 (47:00 to 47:55)	
Rationale for change	Initial wrong planned time on day 3	
	ı	

APPROVAL / SIGNATURE PAGE

Document Number: c15848749 Technical Version Number: 3.0

Document Name: clinical-trial-protocol-revision-02

Title: Safety, tolerability and pharmacokinetics of multiple rising inhaled doses of BI 1265162 in healthy male subjects in a randomised, double blind, placebo-controlled trial

Signatures (obtained electronically)

2. LIST OF ABBREVIATIONS

Term	Definition / description
AE	Adverse Event
AESI	Adverse event of special interest
ALT	Alanine aminotransferase
AST	Aspartate aminotransferase
AUC _{τ,1}	Area under the concentration-time curve of the analyte in plasma over a uniform dosing interval τ after administration of the first dose
AUC _{τ,ss}	Area under the concentration-time curve of the analyte in plasma at steady state over a dosing interval τ
BI	Boehringer Ingelheim
BLQ	Below the lower limit of quantification
BMI	Body mass index
C _{max}	Maximum measured concentration of the analyte in plasma
C _{max,ss}	Maximum measured concentration of the analyte in plasma at steady state
CTP	Clinical Trial Protocol
CTR	Clinical Trial Report
CV	Arithmetic coefficient of variation
ECG	Electrocardiogram
FEF ₂₅₋₇₅	Forced expiratory flow
FEV ₁	Forced expiratory volume in 1 second
FVC	Forced vital capacity
gCV	geometric coefficient of variation
ICH	International Conference On Harmonisation
IPD	Important Protocol Deviation
MedDRA	Medical Dictionary For Regulatory Activities
NOA	Not analysed
NOR	No valid result
NOS	No sample available

Term	Definition / description
PD	Protocol Deviation
PK	Pharmacokinetics
PKS	Pharmacokinetic parameter set
PR	Pulse rate
RAGe	Report appendix generator
RPM	Report Planning Meeting
SAE	Serious adverse event
SD	Standard Deviation
SOC	System Organ Class
TS	Treated set
TSAP	Trial Statistical Analysis Plan
ULN	Upper limit of normal range

3. INTRODUCTION

As per ICH E9 ([1](#)), the purpose of this document is to provide a more technical and detailed elaboration of the principal features of the analysis described in the revised CTP, and to include detailed procedures for executing the statistical analysis of the primary and secondary variables and other data.

This TSAP assumes familiarity with the CTP and its amendments. In particular, the TSAP is based on the planned analysis specification as written in CTP Section 7 "Statistical Methods and Determination of Sample Size". Therefore, TSAP readers may consult the CTP for more background information on the study, e.g., on study objectives, study design and population, treatments, definition of measurements and variables, planning of sample size, randomisation.

Study data will be stored in a trial database within the Oracle ClinicalTM system.

The statistical analyses will be performed within the validated working environment CARE, including SASTM (current Version 9.4, by SAS Institute Inc., Cary, NC, USA), and a number of SASTM-based tools (e.g., macros for the analyses of AE data or laboratory data; Report Appendix Generator system (RAGe) for compilation/formatting of the CTR appendices).

PK parameters will be calculated using Phoenix WinNonlinTM software (version Phoenix 6.3, Certara USA Inc., Princeton, NJ, USA).

4. CHANGES IN THE PLANNED ANALYSIS OF THE STUDY

All analyses described in this TSAP are in accordance with the statistical methods described in the revised CTP.

The secondary endpoint $AUC_{\tau,1}$ (as defined in the CTP) is described as AUC_{0-12} in this TSAP. This is not a change in the planned analysis. Only a more precise parameter name is used.

The definition of baseline ECG is not described properly in the CTP (Section 5.2.4.1). In this TSAP, the derivation of baseline ECG values is described in more detail to clarify how data are analysed. Prior to first study drug administration, 3 triplicate ECGs (9 single ECGs) will be recorded. The mean of the first ECG measurement of each triple ECG will be analysed.

5. ENDPOINTS

5.1 PRIMARY ENDPOINT

Primary endpoint is the number of subjects with drug-related AEs, as defined in Section 5.2.1 of the CTP.

5.2 SECONDARY ENDPOINTS

5.2.1 Key secondary endpoint

Not applicable.

5.2.2 Secondary endpoints

Secondary endpoints of this trial are AUC_{0-12} and C_{max} of BI 1265162 in plasma after the first dose, $AUC_{t,ss}$ and $C_{max,ss}$ of BI 1265162 in plasma after the last dose, as defined in Section 5.5.1.1 of the CTP.

6. GENERAL ANALYSIS DEFINITIONS

6.1 TREATMENTS

For basic study information on treatments to be administered, assignment of treatment groups, and selection of doses, cf. Section 4 of the CTP.

Subjects were planned to be treated either with

- multiple doses of 10, 30, 100, 300, or 600 µg of BI 1265162 (test treatments)
or
- multiple doses of placebo (reference treatment)

The subjects will receive a single dose of BI or placebo in the morning on Day 1 and Day 8. On days 2-7 the subjects will receive the dose of BI or placebo twice daily. For the analysis, the on-treatment period will include all treatment days independent of the number of the total number of doses per day.

All placebo subjects will be analysed in one pooled placebo group (i.e. no distinction between dose groups will be made for placebo subjects).

Analysis phases for statistical analysis of AEs, safety laboratory data, vital signs, spirometry and ECG are defined for each subject as described in the table below.

Table 6.1: 1 Flow chart of analysis phases for statistical analyses of AEs, safety laboratory data, vital signs, spirometry and ECG

Study analysis phase	Label	Start (inclusive)	End (exclusive)
Screening	Screening	Date of informed consent	Date/time of first administration of study drug
On-treatment	Pbo, 10 ug BI, 30 ug BI, 100 ug BI, 300 ug BI, or 600 ug BI, respectively	Date/time of first administration of study drug	Date/time of last administration of BI 1265162 + REP or 12:00 a.m. on day after subject's trial termination date, whichever occurs earlier
Follow-up ¹	F/U Pbo, F/U 10 ug BI, F/U 30 ug BI, F/U 100 ug BI, F/U 300 ug BI, or F/U 600 ug BI, respectively	Date/time of last administration of BI 1265162 + REP	12:00 a.m. on day after subject's trial termination date

¹ Follow-up phases might not exist, e.g. if the subject's trial termination date is within 2 days after last administration of BI 1265162.

CTR Section 15, Appendix 16.1.13.1.8.2 and Appendix 16.1.13.1.8.3 AE displays will present results for the on-treatment phase only.

In CTR Section 15 AE tables (but not in Appendix 16.1.13.1.8.2 and Appendix 16.1.13.1.8.3 AE tables), the following totals will be provided in addition:

- "**Total BI**", defined as the total over all on-treatment phases involving BI
- "**Total on-trt**", defined as the total over all on-treatment phases, including placebo

CTR Appendix 16.1.13.1.8.1 displays will present results for the screening, on-treatment and follow-up phases.

Additionally to the totals defined above, the following total will be provided in CTR Section 16.1.13.1.8.1 AE tables:

- "**Total**", defined as the total over all study phases (screening + on-treatment + follow-up)

More details on the technical implementation of these analyses are provided in the ADS Plan of this TSAP.

6.2 IMPORTANT PROTOCOL DEVIATIONS

Data discrepancies and deviations from the CTP will be identified for all patients entered and randomised who did not fail during screening.

Consistency check listings (for identification of deviations from time windows) and a list of protocol deviations (e.g. deviations in drug administration, in blood sampling times, etc.) will be provided to be discussed at the report planning and database lock meeting (RPM/DBLM). At this meeting, it will be decided whether a discrepant data value can be used in analyses or whether it must be corrected in the clinical database. Each protocol deviation must be assessed to determine whether it is an important protocol deviation (iPD). For definition of iPDs, and for the process of identification of these, refer to the Boehringer Ingelheim (BI) SOP "Integrated Quality and Risk Management Process" ([2](#)).

If any iPDs are identified, they are to be summarised into categories and will be captured in the RPM/DBLM minutes via an accompanying excel spreadsheet. The table below contains the categories which are considered to be iPDs in this trial. If the data show other important PDs, this table will be supplemented accordingly by the time of the RPM/DBLM.

iPDs will be summarised and listed.

Table 6.2: 1 Important protocol deviations

Category / Code	Description
A	Entrance criteria not met
A1	Inclusion criteria violated
A2	Exclusion criteria violated
B	Informed consent
B1	Informed consent not available
B2	Informed consent too late
C	Trial medication and randomisation
C1	Incorrect trial medication taken
C2	Randomisation not followed
C3	Non-compliance
C4	Incorrect intake of trial medication
C5	Incorrect dose of trial medication taken
D	Concomitant medication
D1	Prohibited medication use
E	Missing data
	None ¹
G	Other trial specific important deviation
G1	Certain deviations of procedures used to measure secondary PK data

Deviations C1, C2, C5 and G1 can only be detected at the trial site.

¹ Missing visits, evaluations, and tests will be considered missing data, not protocol deviations

6.3 SUBJECT SETS ANALYSED

All entered subjects who received study medication will be included in the safety analysis and in the PK analysis depending on the availability of measurement values, and on their adherence to the CTP.

The following subject sets will be defined for statistical analysis:

- Treated set (TS):
This subject set includes all subjects who received at least one dose of study drug. This is the full analysis set population in the sense of ICH-E9. It will be used for analysis of safety, demographic data and baseline characteristics.
- Pharmacokinetic parameter set (PKS):
This subject set includes all subjects in the TS who provide at least one PK parameter that was not excluded because of PDs relevant to the statistical evaluation of PK endpoints as defined in Section 7.3 of the CTP.

The discussion of all exceptional cases and problems and the decisions on the allocation of subjects to analysis sets will be made at latest at the RPM/DBLM.

Table 6.3: 1 Subject sets analysed

Class of endpoint	Subject set	
	TS	PKS
Disposition	X	
Exposure	X	
IPDs	X	
Demographic/baseline endpoints	X	
Primary endpoint	X	
Other safety parameters	X	
Secondary PK endpoints		X

6.5 POOLING OF CENTRES

This section is not applicable, because the study was performed in only one centre.

6.6 HANDLING OF MISSING DATA AND OUTLIERS

Data of screened subjects who were withdrawn from the trial prior to first administration of any study drug will not be reported in the CTR.

Data of subjects who failed to complete all periods of the study (dropouts or withdrawals) will be reported in the CTR as far as their data are available. All withdrawals will be documented and the reason for withdrawal recorded in the CTR.

CTP: *With respect to safety evaluations, it is not planned to impute missing values.*

The only exceptions where imputation might be necessary for safety evaluation are AE dates. Missing or incomplete AE dates are imputed according to BI standards ([3](#)).

Missing data and outliers of PK data are handled according to BI standards ([4](#)).

Plasma concentration-time tables

CTP: *Drug concentration data identified with NOS (no sample available), NOR (no valid result), NOA (not analysed) or BLQ (below the lower limit of quantification) will be displayed as such and not replaced by zero at any time point (this rule also applies to the lag phase, including the predose values).*

Pharmacokinetic parameters

CTP: *For tabulation and graphical displays, concentration data identified with NOS, NOR or NOA will generally not be considered. Concentration values in the lag phase identified as BLQ will be set to zero. All other BLQ values of the profile will be ignored. The lag phase is defined as the period between time zero and the first time point with a concentration above the quantification limit.*

6.7 BASELINE, TIME WINDOWS AND CALCULATED VISITS

There will be a centralised evaluation of 12-lead ECG recordings at the time points specified in [Table 6.7: 1](#).

Triple ECGs will be recorded at Visit 2 assessments and will be evaluated by a central lab. At Visit 1 and 3 only single ECGs will be recorded. This data will not be evaluated centrally. At predose (Visit 2, Day 1, planned time point -01:30, notation for data transfer -01:30, -01:25, and -01:20), three triplicate ECGs (9 single ECGs) will be recorded.

For all on-treatment assessments as well as for the 3 predose triplicates, only the first of the 3 replicate ECGs at a single assessment time will be evaluated centrally.

The baseline value of an ECG variable is defined as the mean of the first single ECG measurement of each triple ECG prior to first drug administration.

Table 6.7: 1 Time schedule of 12-lead ECG recordings with centralised evaluation

Visit	Day	Planned time [hh:mm] - relative to respective drug administration	Study phase
2	1	-01:30	Baseline
		00:10	On-treatment
		01:00	
		04:00	
		12:00	
	2	24:10	
	3	48:10	
	5	96:10	
	6	120:10	
	8	164:30	
		168:10	
		169:00	
		172:00	
		180:00	
	9	191:30	

For urine electrolytes there is a whole baseline day to have time matched baseline measurements (see [Table 6.7: 2](#) for details).

In all other analyses the last non-missing value determined prior to the first dosing of BI 1265162 will be defined as baseline.

Time windows are defined in Section 6.1 of the CTP. Adherence to time windows will be checked at the RPM/DBLM.

Unscheduled measurements of laboratory data, vital signs or spirometry data will be assumed to be repeat measurements of the most recent scheduled measurement (e.g. for follow-up or confirmation of a particular value). Therefore, unscheduled measurements will be assigned to the planned time point of the previous scheduled measurement.

Table 6.7: 2 Time schedule of urine electrolyte measurements

Visit	Day	Planned time interval [hh:mm] - relative to respective drug administration (planned time at the day)	Study phase
2	-1	-24:00 to -20:00 (08:00 to 12:00)	Baseline
		-20:00 to -16:00 (12:00 to 16:00)	
		-16:00 to -12:00 (16:00 to 20:00)	
		-12:00 to 00:00 (20:00 to 08:00 on Day 1)	
	5	96:00 to 100:00 (08:00 to 12:00)	On-treatment
		100:00 to 104:00 (12:00 to 16:00)	
		104:00 to 108:00 (16:00 to 20:00)	
		108:00 to 120:00 (20:00 to 08:00 on Day 6)	
	8	168:00 to 172:00 (08:00 to 12:00)	
		172:00 to 176:00 (12:00 to 16:00)	
		176:00 to 180:00 (16:00 to 20:00)	
		180:00 to 192:00 (20:00 to 08:00 on Day 9)	

Descriptive statistics of laboratory data will be calculated by planned time point based on the worst value of the subject at that planned time point (or assigned to that planned time point).

For vital signs and spirometry, descriptive statistics will be calculated by planned time point based on the last value of the subject at that planned time point (or assigned to that planned time point).

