		179:00	19:00	Dinner ³							
		180:00	20:00			x ⁸		Х	Х		х
	9	191:30	07:30				Ī -	X	X		Х
		192:00	08:00		x ¹³	x ¹⁹	_				
		192:30	08:30	Breakfast			 				
		196:00	12:00	Lunch			 				
		200:00	16:00	Snack (voluntary)			 				
		203:00	19:00	Dinner			 				х
	10	216:00	08:30	Breakfast (voluntary) -			†				x x ²⁰
	-			discharge			L				
3	10 to 15	_		End of trial (EOS) examination ⁴	X			X	X		X

- Screening includes subject information, informed consent, physical examination, check of vital signs, 12-lead ECG), safety laboratory (including alcohol breath test, drug screening), demographics (including determination of body height and weight, smoking status and alcohol history), medical history, concomitant therapy and review of inclusion/exclusion criteria.
- 2. The time is approximate; the respective procedure is to be performed and completed within 3 h prior to drug administration. Allocation to treatment may be performed at any time following enrolment but must be completed prior to (first) drug administration.
- 3. If several actions are indicated at the same time point, the intake of meals will be the last action.
- 4. End of trial examination includes physical examination, vital signs, ECG, safety laboratory, recording of AEs and concomitant therapies (if on the same day as Day 10 of visit 2, breakfast and discharge from site will be done after last EOS procedures).
- 5. Only urine drug screening and alcohol breath test will be done at this time point.
- 6. AEs and concomitant therapies will be recorded throughout the trial, but will be specifically asked for at the time points indicated in the Flow Chart above.
- 7. Safety laboratory to be taken and to be medically evaluated within 3 days prior to administration of study drug; this safety laboratory can be omitted, if the screening examination is performed on Days -3, or -2.
- 9. At baseline (i.e. Day 1, prior to drug administration) 3 triplicate ECGs are recorded within approximately one hour. The recordings should be separated by at least 15 minutes.

c15848749-03

04 Jul 2018

Trial Protocol

Page 7 of 84

- 10. The ECG recording has to be performed as triple at this time points (Visit 1 and 3, ECGs as single only)
- 11. Sampling times and periods may be adapted based on information obtained during the trial including addition of samples and visits as long as the total blood volume taken does not exceed 500 mL per subject
- 13. Serum electrolytes only

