6. INVESTIGATIONAL PLAN

6.1 VISIT SCHEDULE

Exact times of measurements outside the permitted time windows will be documented. The acceptable time windows for screening and end of trial examination are given in the Flow Chart.

Study measurements and assessments scheduled to occur 'before' trial medication administration on Days 1 and 8 are to be performed and completed within a 3 h-period prior to the trial drug administration (including blank values for PK).

The acceptable deviation from the scheduled time for vital signs, spirometry, ECG and laboratory tests will be \pm 30 min for the first 4 h after trial drug administration and \pm 45 min thereafter.

If scheduled in the Flow Chart at the same time as a meal, blood sampling, vital signs and 12-lead ECG recordings have to be done first. Furthermore, if several measurements including venipuncture are scheduled for the same time, venipuncture should be the last of the measurements (if at the same time point as spirometry, spirometry should be last measurement) due to its inconvenience to the subject and possible influence on physiological parameters.

For planned individual plasma concentration sampling times and refer to the Flow Chart. While these nominal times should be adhered to as closely as possible, the actual sampling times will be recorded and used for determination of pharmacokinetic parameters.

If a subject misses an appointment, it will be rescheduled if possible. The relevance of measurements outside the permitted time windows will be assessed no later than at the Blinded Report Planning Meeting.

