6.2.3 End of trial period

For AE assessment, laboratory tests, recording of ECG and vital signs, and physical examination during the end of trial period, see Sections 5.2.2 to 5.2.5.

Subjects who discontinue treatment before the end of the planned treatment period should undergo the end of trial visit.

All abnormal values (including laboratory parameters) that are judged clinically relevant by the investigator will be monitored using the appropriate tests until a return to a medically acceptable level is achieved. (S)AEs persisting after subject's end of trial must be followed up until they have resolved, have been sufficiently characterised, or no further information can be obtained.

The end of the trial as a whole is defined by the 'last regular visit completed by last subject' or 'end date of the last open AE' or 'date of the last follow-up test' or 'date of an AE has been decided as sufficiently followed-up', whichever is latest.

c15848749-03

Page 64 of 84

Proprietary confidential information © 2018 Boehringer Ingelheim International GmbH or one or more of its affiliated companies

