7.8.5 Others

Spirometry

CTP: *For [...] spirometry, the differences from baseline will be evaluated.*

Descriptive statistics of spirometry endpoints (FEV₁, FVC and FEF₂₅₋₇₅) over time and their change from baseline will be presented. Additionally, plots over the time will be provided for spirometry data. Individual subject data and the mean per dose group will be presented.

Clinically relevant findings in spirometry data will be reported as AEs and will be analysed as part of AE analysis.

Physical examinations

Physical examination findings will be reported as relevant medical history/baseline condition (i.e., a condition already existent before intake of study drug) or as AE and will be summarised as such. No separate listing or analysis of physical examination findings will be prepared.

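### For vital signs and spirometry, a later recheck can replace a valid abnormal scheduled reading in the by-time-point safety tables

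*SAP*

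**What the plan says.** Two rules in SAP section 6.7 act together. The first concerns what an unscheduled reading is: "Unscheduled measurements of laboratory data, vital signs or spirometry data will be assumed to be repeat measurements of the most recent scheduled measurement". The SAP gives follow-up or confirmation of a particular value as the example, and concludes that "unscheduled measurements will be assigned to the planned time point of the previous scheduled measurement". The second concerns which value is summarised. Spirometry and vital signs share one rule: "descriptive statistics will be calculated by planned time point based on the last value of the subject at that planned time point". Any reading that has been assigned to the time point counts as well. The sentence just before it treats laboratory data differently: "Descriptive statistics of laboratory data will be calculated by planned time point based on the worst value of the subject at that planned time point".

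These values feed the planned tables: vital signs over time and as difference from baseline (SAP 7.8.3), and FEV1, FVC and FEF25-75 over time and as change from baseline (SAP 7.8.5). Spirometry plots are also planned, in which "Individual subject data and the mean per dose group will be presented"; the SAP does not say which value is plotted.

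**The concern.** Readings taken for follow-up or confirmation are usually taken because the scheduled value looked abnormal. Replacement would then depend on the value itself, and on average would favour recovery. Protocol section 6.2.3 adds to this: abnormal values that the investigator judges clinically relevant "will be monitored using the appropriate tests until a return to a medically acceptable level is achieved". If unscheduled readings are used for that, the last one is by design the recovered one.

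Vital signs and spirometry are named safety criteria in protocol section 5.2.1, and the drug is inhaled. A transient post-dose fall in FEV1 is something these tables should be able to show. Under the current rule it can shrink or disappear from the table while the same event appears as an adverse event, so the two parts of the report would disagree.

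**Working it through.** The plan states no figure to reproduce. There are three steps.

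**1. How far a reading can be carried back.** The only bound is the next scheduled measurement. From the protocol Flow Chart, doses fall at 0 h, every 12 h from 24 to 156 h, and at 168 h.

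| Variable | Interval | Gap | Doses inside |
|---|---|---|---|
| Spirometry | 2:00 to 100:00 | 98 h | 7 (24, 36, 48, 60, 72, 84, 96) |
| Spirometry | 100:00 to 168:20 | about 68 h | 6 (108, 120, 132, 144, 156, 168) |
| Vital signs | 48:10 to about 96:15 | about 48 h | 4 (60, 72, 84, 96) |
| Vital signs | 120:10 to 164:30 | about 44 h | 3 (132, 144, 156) |

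No spirometry is scheduled after 170:00. Flow Chart footnote 4 reads "End of trial examination includes physical examination, vital signs, ECG, safety laboratory, recording of AEs and concomitant therapies" and does not include it. If the end-of-trial visit is on Day 15 at 08:00 (336:00), that leaves 336 - 170 = 166 h. The Day 5 Flow Chart rows may be displaced in the PDF text (96:15 there, 96:10 for ECG in SAP Table 6.7: 1), so the gaps are approximate.

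**2. Arithmetic for one subject.** Assume 8 active subjects, of whom one falls 20% at the scheduled reading and seven are at 0.

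| Value tabulated | Mean | Minimum |
|---|---|---|
| Scheduled | -20/8 = -2.5% | -20% |
| Recheck, half recovered | -10/8 = -1.25% | -10% |
| Recheck, fully recovered | 0 | 0 |
| Recheck worse, at -25% | -25/8 = -3.1% | -25% |

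**3. Range under an assumed distribution.** Scheduled change x ~ N(-5, 6) in per cent, n = 8. A recheck follows if x is at or below minus the trigger (10, 15 or 20%), with probability 0.5 or 1. Recheck = (1 - r)x + N(0, 3), with r = 0.5 or 1. This gives 12 scenarios, each with 200,000 simulated groups. Every input is an assumption.

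- Scheduled values: mean -5.0%. With a = (-10 + 5)/6 = -0.833 and Φ(a) = 0.202, the chance that the table minimum shows a fall of 10% or more is 1 - (1 - 0.202)^8 = 84%.
- Extreme case (10% trigger, all rechecked, full recovery): mean = μ(1 - Φ(a)) + σφ(a) = -5 × 0.798 + 6 × 0.282 = -2.3%, and the chance falls to 0.1%. The mean is -3.0% at SD 5 and -1.65% at SD 7.
- 10% trigger, half rechecked, full recovery: about -3.7% and 57%.
- 15% trigger, all rechecked, full recovery: -4.2% and 74%.
- Across the 12 scenarios: mean from -2.3% to -5.0%, chance from 0.1% to 83%.
- Outside those 12, with a 10% trigger and all rechecked: -5.0% with no recovery, and -5.7% if rechecks are 25% worse.

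**The case against.** The strongest objection is that the signal is captured elsewhere. The follow-up requirement in protocol section 6.2.3 sits in the end-of-trial section and covers only values judged clinically relevant. Those values are reported as adverse events and, if drug-related, count in the primary endpoint. No document requires a recheck of other abnormal values. This stands and limits the weight of the point, but it does not correct the tables.

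Second, review could catch a late reading. Protocol section 6.1 sets windows ("The acceptable deviation from the scheduled time for vital signs, spirometry, ECG and laboratory tests will be" ±30 min for the first 4 h after dosing and ±45 min after that) and has measurements outside them assessed by the report planning meeting. SAP section 6.2 lets that meeting decide whether a discrepant value can be used. Neither names unscheduled readings, so this is case-by-case discretion. A recheck taken soon after the scheduled reading would not even be out of window.

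Third, the last value is a defensible choice for blood pressure and pulse, where worst has two directions. That argues against copying the laboratory rule, but not against keeping the scheduled reading.

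Fourth, the simulation is only illustrative. It models neither placebo, to which the same rule applies, nor vital signs. If part of the SD of 6 is measurement error, some of the apparent loss is regression to the mean. These limits stand. The conclusion rests on the wording of the rules and the one-subject arithmetic.

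**Conclusion.** The concern holds. Followed exactly, SAP section 6.7 lets a recovered recheck displace a valid abnormal scheduled reading, in some cases one taken days and several doses later. With eight active subjects per group, one such replacement can halve or remove the mean change and take the extreme value out of the table. How often this would happen cannot be derived from the documents. Under the assumed inputs, the effect runs from negligible (high trigger, few rechecks) to more than half of the mean change (-5.0% to -2.3%). The direction is not fixed, and there is no effect without rechecks.

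Individual values remain listed (SAP section 7), and the dose-escalation review does not depend on the rule. This is a moderate point about descriptive safety tables that should be corrected because the correction is cheap.

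**What to change.** In SAP section 6.7, base the by-time-point statistics for vital signs and spirometry on the valid reading taken at the scheduled time, within the protocol section 6.1 window. Let a repeat replace it only if the scheduled reading was technically invalid. List unscheduled readings at their actual times, and include them in an added worst post-baseline summary by treatment group: lowest FEV1 and FVC, and both highest and lowest blood pressure and pulse rate. State in SAP section 7.8.5 that the spirometry plots use the same scheduled value as the tables.

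The cost is about three SAP sentences, a changed record-selection flag and one extra table. No new data are needed.
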